5.2.5 Sleep Disorders Inventory

The SDI is assessed at Baseline, Week 4, and Week 8/ET.

The SDI is an expanded version of one item of the Neuropsychiatric Inventory (NPI). It consists of the 7 subquestions from the NPI sleep disturbance item. Each of the subquestions was made into a separate question with frequency, severity, and caregiver distress rated by the caregiver with respect to the patient-participant for the 2 weeks prior to the visit. Thus, in contrast to a single rating for frequency and severity for all sleep disturbance-related behaviors, which would be incorporated into an overall NPI score, the SDI score is derived after the caregiver rates the frequency and severity of each of the 7 separate sleep disturbance symptoms. Caregiver distress ratings are not part of the SDI total score, but distress is measured. The SDI total score is calculated as the average of seven frequency ratings × average of seven severity ratings; thus, the total score has a range of 0-12 (higher scores indicate more severe sleep disorder).

If one frequency rating and/or one severity rating is missing then the total score will be imputed as the average of the non-missing frequency ratings × the average of the non-missing severity ratings. Otherwise, the total score will not be derived.

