6.2.2 EQ-5D-5L

The EQ-5D-5L is a standardized instrument used as a measure of health outcome (Kind 1996). It measures 5 dimensions (mobility, self-care, usual activities, pain/discomfort, anxiety/depression) each of which has 5 potential responses. The responses record 5 levels of severity (no problems/slight problems/moderate problems/severe problems/extreme problems) within a particular EQ-5D dimension. The EQ-5D-5L Proxy version 1 will be used. For this version, a caregiver (the proxy) is asked to rate the subject's health-related

quality of life in their (the proxy's) opinion. The EQ-5D-5L will be assessed at Weeks 0 and 8/EOT and will be used for exploratory efficacy analyses.

6.2.3 **Sleep Disorders Inventory**

The SDI is an expanded version of one item of the NPI (Tractenberg et al. 2003). It consists of the 7 subquestions from the NPI sleep disturbance item. Each of the subquestions was made into a separate question with frequency, severity, and caregiver distress rated by the caregiver with respect to the patient-participant for the 2 weeks prior to the visit. Thus, in contrast to a single rating for frequency and severity for all sleep disturbance-related behaviors, which would be incorporated into an overall NPI score, the SDI score is derived after the caregiver rates the frequency and severity of each of the 7 separate sleep disturbance symptoms. Caregiver distress ratings are not part of the SDI total score, but distress is measured. The SDI total score is calculated as the average of seven frequency ratings × average of seven severity ratings, with a range of 0-12. The SDI will be assessed at Weeks 0, 4, and 8/EOT and will be used for exploratory efficacy analyses.

6.3 **Safety Assessments**

6.3.1 **Physical Examinations**

A physical examination will be conducted.

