5.2.1 Neuropsychiatric Inventory

The Neuropsychiatric Inventory (NPI) is assessed at Screening and Baseline.

The NPI was developed to assess psychopathology in dementia patients. The original NPI evaluated 10 neuropsychiatric disturbances common in dementia: delusions (domain A), hallucinations (domain B), agitation/aggression (domain C), depression/dysphoria (domain D), anxiety (domain E), elation/euphoria (domain F), apathy/indifference (domain G), disinhibition (domain H), irritability/lability (domain I), and aberrant motor behavior (domain J). Two additional domains, sleep (domain K) and appetite and eating disorders (domain L), were subsequently added to the NPI. At Screening, the degree of the patient's neuropsychiatric symptoms will be evaluated using several of the domains of the NPI (delusions, hallucinations, depression/dysphoria, apathy/indifference, disinhibition, irritability/lability, and sleep). Patients with at least one individual domain score (frequency ×

severity) greater than or equal to 4 at Screening and Baseline (the domains at Screening and Baseline can be different) will be eligible for the study.

Individual domain total scores are calculated as frequency × severity. Missing scores will not be imputed. Thus, if either the frequency or severity is missing for a given domain then the domain total score will be missing.

Each domain has an associated caregiver distress question, rated on a 5 point scale from 0=no distress to 5=very severe or extreme. The caregiver distress items will not be summarized but will be displayed in data listings.

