13.4.3 SDI

Observed SDI scores will be summarized using descriptive statistics at Baseline, Week 4, and Week 8/ET. The change from Baseline values will be summarized descriptively at Week 4 and Week 8/ET. The change from Baseline in SDI score will also be analyzed using the MMRM model as described in Section 13.2.

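### SAP 5.2.5 fills in a missing SDI rating without using the companion rating of the same symptom: avoidable noise in an exploratory endpoint, not a demonstrated bias

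*SAP*

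**What the plan says.** Protocol 6.2.3 and SAP 5.2.5 describe the same instrument: "the SDI score is derived after the caregiver rates the frequency and severity of each of the 7 separate sleep disturbance symptoms". Both use the same total; the protocol gives it as "average of seven frequency ratings × average of seven severity ratings, with a range of 0-12". The protocol has no rule for missing ratings, so SAP 5.2.5 is the only instruction. It applies when at most one frequency and at most one severity are missing: "If one frequency rating and/or one severity rating is missing then the total score will be imputed as the average of the non-missing" ratings of each kind. In full, the replacement is "the average of the non-missing frequency ratings × the average of the non-missing severity ratings. Otherwise, the total score will not be derived".

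Neither document gives the item maxima or says how an absent symptom is recorded. The SAP states only the range of the total: "thus, the total score has a range of 0-12 (higher scores indicate more severe sleep disorder").

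For the Neuropsychiatric Inventory (NPI), whose domain scores are also frequency times severity, SAP 5.2.1 does not impute: "if either the frequency or severity is missing for a given domain then the domain total score will be missing". SAP 5.2.5 describes the SDI as an expansion of one NPI item.

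On use of the score, SAP 13.4.3 says: "The change from Baseline in SDI score will also be analyzed using the MMRM model as described in Section 13.2".

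**The concern.** Averaging over the available items is reasonable when nothing is known about the missing one. Here each rating has a companion on the same symptom, and the companion often says whether the symptom is present. The SAP rule keeps the companion in its own seven-item average but does not use it to inform the missing rating. Two results conflict with the recorded data:

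- The companion is 0, so the symptom is absent and the exact total is known. The rule still divides by six in place of seven and overstates the total.
- The companion is above 0, so the symptom is present. The missing rating takes the average of the other six symptoms. If those are all 0, the total is 0, the best possible score.

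The SDI change from Baseline goes into the MMRM of SAP 13.2 with the Baseline score and its interaction with visit as covariates. A mis-scored Baseline therefore affects the covariate and both the Week 4 and Week 8 changes. SAP 13.2 attaches confidence intervals, p-values and effect sizes to these results.

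**Working it through.** **Inputs.** Seven symptoms, each with a frequency F and a severity S; total = (sum of F / 7) × (sum of S / 7); range 0-12 (SAP 5.2.5, Protocol 6.2.3).

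**Assumptions.** An absent symptom is rated 0 on both ratings. A total of 0 is possible only if all seven frequencies or all seven severities can be 0. Item maxima are taken as 4 for frequency and 3 for severity. The documents give only the range, which requires a product of 12; the totals for symptoms at maximum depend only on that product.

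**The plan's own figure.** All ratings 0 gives 0; all at maximum gives 4 × 3 = 12. The range is consistent with the formula, but without stated item maxima it cannot be reproduced independently.

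**Missing rating, companion 0.** Let A be the sum of the frequencies and B the sum of the severities. The true total is (A/7)(B/7). With the frequency of an absent symptom missing, the rule gives (A/6)(B/7). The ratio is 7/6 = 1.167 for any non-zero total, and the same holds for a missing severity.

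**Missing rating, companion above 0.** With k symptoms at maximum and the frequency of one of them missing, the rule gives (4(k−1)/6)(3k/7) against the true (4k/7)(3k/7). The ratio is 7(k−1)/(6k).

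| k present | True total, 12k²/49 | SAP total, companion 0 | Error | SAP total, companion above 0 | Error |
|---|---|---|---|---|---|
| 1 | 0.245 | 0.286 | +0.041 | 0 | −0.245 |
| 2 | 0.980 | 1.143 | +0.163 | 0.571 | −0.408 |
| 3 | 2.204 | 2.571 | +0.367 | 1.714 | −0.490 |
| 4 | 3.918 | 4.571 | +0.653 | 3.429 | −0.490 |
| 5 | 6.122 | 7.143 | +1.020 | 5.714 | −0.408 |
| 6 | 8.816 | 10.286 | +1.469 | 8.571 | −0.245 |
| 7 | 12.000 | not possible | – | 12.000 | 0 |

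For a lone symptom below maximum, the true total is F × S/49, from 1/49 = 0.020 to 12/49 = 0.245.

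**Average error.** Suppose one frequency is missing and each of the seven symptoms is equally likely to be the one affected. The expected mean frequency under the rule is (1/7) × Σ(A − Fj)/6 = (7A − A)/42 = A/7, which is the true mean. At k=1 the ratio to truth is 1/7 × 0 + 6/7 × 7/6 = 1. At k=6 the expected error is 6/7 × (−0.245) + 1/7 × 1.469 = 0. The cancellation covers one missing rating. If both ratings of an absent symptom are missing, the factor is (7/6)² = 1.361, and at k=1 the expected ratio is 6/7 × 1.361 = 1.167. In that case, though, no companion rating exists to contradict the score.

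**Rule proposed below.** With companion 0 the total is exact. With companion above 0 and k of at least 2, the frequency sum becomes (A − Fj) + (A − Fj)/(k−1) = (A − Fj) × k/(k−1). Its average over the k present symptoms is A, so the rule stays correct on average under the same assumption. For k=2 at maximum it gives (8/7)(6/7) = 0.980 in place of 0.571.

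**Dependence on coding.** If absent symptoms carried severity 1, the lone-symptom case would be 0 against (4/7)(9/7) = 0.735. If they carried frequency 1, it would be (6/6)(3/7) = 0.429 against (10/7)(3/7) = 0.612. If absent symptoms were left blank, two or more blanks of one kind would mean no total at all.

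**The case against.** The best defence is that the rule is leave-one-out averaging, and that its upward and downward errors are two halves of an estimator that is right on average. That stands for a single missing rating under the equal-likelihood assumption. What remains is noise in individual scores.

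The rule is also limited to one missing rating of each kind, and the SAP prorates the ESRS-A (5.2.8) and MMSE (5.2.9) in a similar way. The comparison is only partial: those totals are sums of single ratings, with no companion to contradict the imputation. Protocol 10.3 requires eCRF omissions to be explained, so isolated blanks should be uncommon. The endpoint is exploratory.

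An obvious remedy is to copy the NPI rule and drop every total whose missing rating has a companion above 0. The objection to that is sound. Under equal likelihood, an affected assessment would be kept with probability (7−k)/7: 86% at k=1 and 14% at k=6. Take affected assessments split equally between k=1 and k=6 at maximum. The true mean is (0.245 + 8.816)/2 = 4.53. The mean of those kept would be (6/7 × 0.245 + 1/7 × 8.816)/(6/7 + 1/7) = 1.47. That selects against high sleep burden and strains the missing-at-random assumption in SAP 13.2.

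The defence does not justify keeping a value that the recorded data show to be wrong when the exact one can be computed.

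**Conclusion.** The point holds as a minor scoring defect. It rests on the inferred coding of an absent symptom as 0, which the SAP should state. With companion 0, the excess is 16.7% of any non-zero total and reaches 1.47 points only with six symptoms at maximum. The lone-symptom error is at most 0.245 points, about 2% of the scale (0.245/12).

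A reader might infer that the rule biases the SDI treatment comparison, or that subjects with serious sleep disturbance are scored as resolved. The documents support neither. Nothing in them suggests that missing ratings differ by arm or fall more often on present symptoms. A subject wrongly scored 0 has one symptom and a true total close to the floor. The number of incomplete assessments is not given and is probably small.

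**What to change.** In SAP 5.2.5, state how an absent symptom is coded and the item maxima. Keep the limit of one missing frequency and one missing severity, and replace the single rule with three cases:

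1. One rating of a symptom is missing and its companion is 0: set the missing rating to 0 and compute the total.
2. One rating is missing and its companion is above 0: impute it as the mean of that rating over the subject's other present symptoms at that visit. Leave the total underived only when no other symptom is present.
3. Both ratings of the same symptom are missing: keep the current averaging.

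Do not drop every total in case 2, for the selection reason given above.

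The cost is SAP wording, a few lines of derivation code and an occasional underived total. The totals lost are those of subjects whose only present symptom is the affected one, so their true totals are at most 0.245. If this happens at Baseline, the subject also loses the SDI change scores. Case 3 leaves the 36.1% inflation when both ratings of an absent symptom are missing, because nothing recorded on that symptom can correct it.

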5.2.6 Columbia-Suicide Severity Rating Scale

The C-SSRS will be used to assess suicidal ideations and behaviors in subjects who are able to complete the assessment (subjects without dementia, defined as an MMSE≥25, and subjects with dementia who the Investigator has determined can complete the C-SSRS). The C-SSRS is assessed (when applicable) at Screening, Baseline, Weeks 1, 2, 4, 6, and Week 8/ET visits .

The C-SSRS monitors changes in suicidal thinking and behavior over time, in order to determine risk. Four constructs are measured: the severity of ideation, the intensity of ideation, behavior, and lethality.

For subjects who are able to complete the assessment, the Baseline/Screening version will be administered at Screening, and the Since Last Visit version will be administered at subsequent visits. The C-SSRS results for each subject should be reviewed by the Investigator at each visit. If at any time the C-SSRS results for a given subject reveal potential suicidality, then the Investigator should assess the clinical significance of such results. If a clinically significant risk of suicidality is identified for a subject, then the Investigator should discontinue the subject and implement appropriate treatment.

There are 5 questions about suicidal ideation, representing 5 types of suicidal ideation: wish to be dead; non-specific active suicidal thoughts; active suicidal ideation with any methods (not plan) without intent to act; active suicidal ideation with some intent to act, without specific plan; active suicidal ideation with specific plan and intent. If a subject answers "yes" to any of these 5 questions, this subject will be counted as having suicidal ideation.

There are 5 questions about suicidal behavior, representing 5 types of suicidal behavior: preparatory acts or behavior; aborted attempt; interrupted attempt; actual attempt; suicide. If a subject answers "yes" to any of these 5 questions, this subject will be counted as having suicidal behavior.

Missing C-SSRS item scores will not be imputed.

5.2.7 Global Clinician Assessment of Suicidality

If the subject is not able to reliably complete the C-SSRS in the Investigator's judgment, the GCAS will be administered and used thereafter in the study. The GCAS is assessed (when applicable) at Screening, Baseline, Weeks 1, 2, 4, 6, and Week 8/ET visits.

If the GCAS is administered at Visit 1 (Screening) lifetime suicidality and suicidality for the past 3 months will be assessed and at all other visits, suicidality since the previous visit will be assessed. As with the C-SSRS, if at any time the GCAS results for a given subject reveal potential suicidality, then the Investigator should assess the clinical significance of such results. If a clinically significant risk of suicidality is identified for a subject, then the Investigator should discontinue the subject and implement appropriate treatment.

The GCAS is a clinician-rated, 5-point scale that is designed to rate the subject's suicidality based on the report of the subject, the report of the study partner/caregiver, and the clinician's global assessment. Ratings can be 0 ("Absent"), 1 ("Feels life is not worth living"), 2 ("Wishes he/she were dead or any thoughts of possible death to self"), 3 ("Suicidal ideas or gesture"), or 4 ("Attempt at suicide"). The Investigator will record a subject rating, a study partner/caregiver rating, and a clinician rating.

Missing scores will not be imputed.

5.2.8 Extrapyramidal Symptom Rating Scale-Abbreviated

The ESRS-A is assessed at Baseline, Weeks 1, 2, 4, 6, and Week 8/ET.

The ESRS was developed to assess 4 types of drug-induced movement disorders (Parkinsonism, akathisia, dystonia, and tardive dyskinesia) with established reliability, validity, and sensitivity. The ESRS-A, an accepted modified form of the original ESRS, will be used during the study to monitor for any worsening in extrapyramidal symptoms or signs at scheduled and unscheduled visits.

The ESRS-A consists of 4 subscales and 4 clinical global impression movement severity (CGI-S) scales of Parkinsonism, dyskinesia, dystonia, and akathisia.

The Parkinsonism subscale consists of 10 items, the dyskinesia subscale consists of 6 items, the dystonia subscale consists of 6 items, and the akathisia subscale consists of 2 items. Each item is scored on a 6-point scale: 0=absent; 1=minimal; 2=mild; 3=moderate; 4=severe; 5=extreme. The ESRS-A total score is the sum of the 24 item scores with a possible range of 0 to 120. Higher scores denote more severe drug-induced movement disorders.

Each CGI-S scale of Parkinsonism, dyskinesia, dystonia, and akathisia is a single-item 6-point scale: 0=absent; 1=minimal; 2=mild; 3=moderate; 4=severe; 5=extreme, with higher scores indicating more severe movement disorders.

If 4 or fewer items are missing, then the total score for a given subject and timepoint will be imputed as the mean of the non-missing items multiplied by 24 and rounded to the nearest integer. If more than 4 items are missing, the total score will not be derived. Missing ESRS-A item scores and subscale total scores of the 4 subscales will not be imputed. Missing CGI-S scores will not be imputed.

5.2.9 Mini-Mental State Examination

The MMSE is assessed at Screening, Baseline, Weeks 1, 2, 4, 6, and Week 8/ET visits.

The MMSE is a 30-item questionnaire that includes simple questions and problems in the following areas: time and place of testing, repeating lists of words, arithmetic, language use and comprehension, and copying or drawing.

Each of the 30 items has 2 possible values: 0=incorrect; 1=correct. The MMSE total score will be derived as the sum of the 30 item scores, thus the total score has a potential range of 0 to 30. Lower scores indicate more severe cognitive impairment.

If 6 or fewer items are missing, then the total score for a given subject and timepoint will be imputed as the mean of the non-missing items multiplied by 30 and rounded to the nearest integer. If more than 6 items are missing, the total score will not be derived.

5.3 Analysis Visit Windows

Baseline of the study is defined as the last non-missing result, included results from repeated and unscheduled measurements, before first dosing of study drug.

Efficacy and safety assessments will be summarized by analysis visit as presented in Table 2 below.

Table 2 Analysis Visit Windows

Analysis Visit Name	Target Study Day ¹	Study Day Interval
Baseline	1	≤1
Week 1	8	2 to 11
Week 2	15	12 to 21
Week 4	29	22 to 35
Week 6	43	36 to 49
Week 8	57	50 to 63
Follow-up	85	64 to maximum

If the assessment date \geq first dose date, study day = assessment date - first dose date + 1, otherwise study day = assessment date - first dose date. Study day 1 is the date of first dose of study drug.

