5.3.1 Unscheduled Assessments

Both scheduled and unscheduled assessments, including early termination visits, will be considered for planned timepoint summaries. All assessments will be presented in data listings.

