12.3 Handling of Missing Data

For selected endpoints missing values will be imputed with the previous observed value (including Baseline) for that subject, i.e. last observation carried forward (LOCF).

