13.2 Mixed Model Repeated Measures (MMRM)

The MMRM method will be used for selected continuous exploratory endpoints, in which missing data is assumed to be missing at random. The dependent variable will be the change from Baseline. The independent variables in the model will include the fixed categorical effects of treatment group, region, visit, and treatment-by-visit interaction, as well as the continuous, fixed covariates of Baseline score and Baseline score-by-visit-interaction. An unstructured covariance matrix will be used to model the within patient errors, and the Kenward-Roger approximation will be used to adjust the denominator degrees of freedom. Observed cases will be analyzed in the model and least squares (LS) means will be estimated using observed margins.

In the event that the model fails to converge using the unstructured covariance matrix, then the following covariance structures will be modeled in the following order:

1) Heterogeneous Toeplitz

- 2) Heterogeneous compound symmetry
- 3) Heterogeneous autoregressive(1)
- 4) Toeplitz
- 5) Compound symmetry
- 6) Autoregressive(1)
- 7) Variance components

The first covariance structure that allows for convergence will be selected for the final model. For change from Baseline values at each post-Baseline visit, LS means, standard errors (SEs), and the between-group difference in LS means with the corresponding two-sided 95% confidence intervals (CIs), p-values, and effect sizes will also be presented. LS means ±SE over time for the change from Baseline values by treatment group will be presented in line plots.

At each visit, the effect size (Cohen's d) for the change from Baseline between the treatment groups will be calculated using the following formula:

$$Effect \ size = \frac{LS \ mean \ difference}{\sqrt{variance}}$$

The variance at a given visit will be obtained from the covariance matrix estimated for the MMRM model. The sign (+ or -) of the effect size will be chosen so that a positive value favors pimavanserin.

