13.3 Analysis of Covariance (ANCOVA)

For those endpoints that are analyzed using ANCOVA (i.e., EQ-5D-5L VAS), the dependent variable will be the change from Baseline, and the independent variables in the model will include treatment group and region as factors, and Baseline score as a continuous covariate. LS means will be estimated using observed margins; the LSM, SE, LSM treatment difference, 95% CI of treatment difference, and p-value for treatment differences from the ANCOVA model will be reported. Observed cases excluding missing values, and the last observation carried forward (LOCF) method of imputation for missing data will be used. If necessary, the Baseline value will be carried forward.

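### SAP Table 2's common visit windows assign many early-termination SDI values to Weeks 1, 2 or 6, where SDI is not analysed; SDI-specific windows would be a cheap improvement

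*SAP*

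**What the plan says.** SAP 5.3 assigns all measures to visits by study day: "Efficacy and safety assessments will be summarized by analysis visit as presented in Table 2 below". Table 2 has Week 1 = Days 2-11, Week 2 = 12-21, Week 4 = 22-35, Week 6 = 36-49 and Week 8 = 50-63. It has no ET row and no windows for individual scales.

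SAP 5.3.1 brings ET visits into the same scheme: "Both scheduled and unscheduled assessments, including early termination visits, will be considered for planned timepoint summaries".

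SDI is not measured at every visit. SAP 13.4.3 states: "Observed SDI scores will be summarized using descriptive statistics at Baseline, Week 4, and Week 8/ET". Its change from Baseline is analysed with the MMRM of SAP 13.2, where "Observed cases will be analyzed in the model" and missing data are assumed missing at random.

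SAP 12.3 offers a carry-forward rule without listing where it applies: "For selected endpoints missing values will be imputed with the previous observed value". The only endpoint for which LOCF is then specified is EQ-5D-5L (SAP 13.3 and 13.4.4).

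The caregiver's SDI rating is retrospective: "rated by the caregiver with respect to the patient-participant for the 2 weeks prior to the visit" (SAP 5.2.5).

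**The concern.** The windows suit scales measured at Weeks 1, 2, 4, 6 and 8. For SDI, three of the five post-Baseline windows lead to visits that the SDI analysis does not contain. Protocol 4.4 asks sites to make every reasonable effort to complete the ET evaluations, and SDI is one of them. Yet for most withdrawal days the stated rules give the resulting SDI no place in the summary or the model.

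The values most worth having come from subjects who leave on Days 15-21. Their two-week recall lies wholly after first dose, but under Table 2 they have no post-Baseline SDI in the MMRM. Their outcome at withdrawal is left to the missing-at-random assumption although it was measured.

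**Working it through.** **Plan's own figure.** SAP 3.5 and protocol 9.3 give 750 randomized, 30% dropout and 525 completers: 750 x (1 - 0.30) = 525, which reproduces. Dropouts = 750 - 525 = 225.

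**Which days are stranded.** An ET SDI reaches an SDI row only on Days 22-35 or 50-63. Days 2-21 map to Week 1 or 2, and Days 36-49 map to Week 6.

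**Proposed windows.** Table 2 gives a midpoint day to the later visit: (15+29)/2 = 22 goes to Week 4, (29+43)/2 = 36 to Week 6, (43+57)/2 = 50 to Week 8. With SDI's own targets, (29+57)/2 = 43 starts Week 8 and (1+29)/2 = 15 starts Week 4. Day 15 is also the first day whose two-week recall does not reach before first dose. Starting there is a choice, because Table 2 opens its own first post-Baseline window at Day 2.

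**Counts.** The documents give no dropout timing, so three assumed shapes are shown. All assume ET on Days 2-57, full ET attendance and no missed scheduled visits. Count = 225 x (sum of weights over the day range) / (sum of weights over Days 2-57). Weights: uniform, 1 (sum 56); late-weighted, the day number (sum 1652); front-loaded, exp(-day/20).

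| ET day | Table 2 visit | With SDI windows | Uniform | Late | Front |
|---|---|---|---|---|---|
| 2-14 | Week 1 or 2 | not used | 52.2 | 14.2 | 114.5 |
| 15-21 | Week 2 | Week 4 | 28.1 | 17.2 | 36.9 |
| 36-42 | Week 6 | Week 4, scheduled value normally wins | 28.1 | 37.2 | 12.9 |
| 43-49 | Week 6 | Week 8 | 28.1 | 43.9 | 9.1 |
| Stranded under Table 2 | | | 137 | 112 | 173 |
| Brought in (15-21 plus 43-49) | | | 56 | 61 | 46 |
| Share brought in | | | 41% | 54% | 27% |
| Still unused | | | 80 | 51 | 127 |

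Examples: uniform, Days 15-21 = 7/56 x 225 = 28.1; late-weighted, Days 43-49 = 322/1652 x 225 = 43.9. At 50% ET attendance every count halves.

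On Days 36-42 the scheduled Week 4 value normally wins because the visit window is ±3 days. It then lies at most 3 days from Day 29, against at least 36 - 29 = 7 for the ET value.

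**Effect on the model (uniform).** Subjects with any post-Baseline SDI in the model: 750 - 80.4 = 669.6, rising to 697.8. Subjects with a Week 8 SDI: 525 + 8/56 x 225 = 557.1, rising to 585.3; most of those added already have a Week 4 value.

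**Precision.** This used a simulated two-visit generalised least squares model with treatment-by-visit, Baseline-by-visit and region, covariance taken as known, 750 subjects and 60 designs per cell. With uniform dropout and an assumed Week 4-Week 8 correlation of 0.6, the SE of the Week 8 difference goes from 0.0824 to 0.0804 SD: 1 - 0.0804/0.0824 = 2.4%. Over the three shapes and correlations 0.4, 0.6 and 0.8, the reduction is 1.2% to 3.2%.

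**Responsiveness.** If ET values in one arm's dropouts were 1 residual SD worse, the Week 8 difference would move 0.081 SD under Table 2 and 0.152 SD under the SDI windows (uniform, correlation 0.6). Over the grid the ranges are 0.032-0.129 and 0.071-0.211.

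**Fitting Weeks 1, 2 and 6 as extra SDI visits instead.** Apart from occasional scheduled visits held out of window, those cells hold dropouts with no later SDI. The covariances that an unstructured matrix needs then have little or no data. SAP 13.2 falls back to simpler forms ("The first covariance structure that allows for convergence will be selected for the final model"), but in one simulated trial with compound symmetry (0.6, uniform dropout) the extra visits left the Week 8 SE at 0.0825. A 3 SD shift of those ET values in one arm moved the Week 8 difference by 0.000.

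**Cost in timing.** Largest distance before target: Table 2, 29 - 22 = 7 and 57 - 50 = 7 days; SDI windows, 29 - 15 = 14 and 57 - 43 = 14 days.

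**The case against.** **Loss of data is inferred.** A reader might infer that the SAP discards these SDI values. It does not say so: all assessments are listed, and the table specifications (SAP 1) and programming conventions (SAP 5.3.2) are separate documents that may add a rule. That limit stands. The available text still leads to rows that SDI lacks, and the conventions are cited for multiple or incomplete assessments within a window, which is a different case.

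**The Week 8/ET label may already pool ET with Week 8.** The same label is used for scales measured at every visit (CGI-S, ESRS-A, MMSE), so it reads as a visit name. Pooling would also conflict with Table 2: the Week 8 row would hold 525 + 225 = 750 subjects instead of about 557 (532 to 583 over the three shapes).

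**The fix is partial.** This stands. Days 2-14 stay out, Days 36-42 normally lose to the scheduled Week 4 value, and 51 to 127 withdrawal outcomes remain unused.

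**The wider windows could add bias.** This stands too. Day 43 is Table 2's own Week 6 target, and counting it as Week 8 could bias the Week 8 estimate if SDI changes over time. That bias has not been measured.

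**The 0.08 and 0.15 SD shifts do not prove Table 2 biased.** A reader might take them that way, but they show only that the wider windows respond more to an assumed difference at withdrawal. Nothing in the documents supports that 1 SD difference.

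**Conclusion.** The point holds as a minor, inexpensive improvement. Followed as written, Table 2 leaves an ET SDI on Days 2-21 or 36-49 without an analysis row, and neither the observed-case MMRM nor the LOCF specified for EQ-5D-5L picks it up. About 112 to 173 values are affected, and SDI windows would recover 46 to 61 of them. These counts rest on the planned 30% dropout, full ET attendance and assumed timing. The precision gain is negligible; the benefit is that some measured withdrawal outcomes enter the model.

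The reach is limited. SDI is exploratory (SAP 12.1), and its p-values are nominal and unadjusted (SAP 12.4, 21.1). TEAEs, ESRS-A and MMSE are unaffected. The observed-case EQ-5D-5L analysis shares the gap, for ET on Days 2-49, but has LOCF as a stated fallback. The documents do not support a claim that the SDI result is biased.

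**What to change.** Add an SDI-specific pair of windows to SAP Table 2: Week 4 = Days 15-42 and Week 8 = Days 43-63. Keep the closest-to-target rule of SAP 5.3.2. State that ET values are assigned by study day, and label the row Week 8 in place of Week 8/ET. Also show the SDI result under the original Table 2, so that the effect of the wider windows is visible.

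The cost is two windows, one sentence, row labels, programming and one extra SDI output. The price in interpretation is the 14-day maximum distance from target. Interim analysis 1 has already used unblinded data from 288 subjects (SAP 16.2), so the rule should be finalised before final unblinding.
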